## PROTOCOL AMENDMENT, VERSION 6: RATIONALE

Protocol WO29519 has been amended to include the addition of an interim overall survival (OS) analysis. Changes to the protocol, along with a rationale for each change, are summarized below:

- Table 1 has been removed and the reader has been referred instead to the Idasanutlin Investigator's Brochure, which contains the most recent information on completed and ongoing studies with idasanutlin (Section 1.2.1).
- The secondary and exploratory endpoints have been updated to also assess the efficacy of treatment in *FLT3*, *IDH1*, and *IDH2*-mutated AML subpopulations, since these have become clinically actionable with targeted treatment (Sections 2.2, 2.3, 3.3.5, 3.4.3, 6.4.2, and 6.4.3).
- An interim efficacy analysis has been added to allow early testing of OS in the event of relevant efficacy, which could influence faster access to study drug for patients (Sections 3.1 and 6.11).
- The total length of study has been revised to 5.5 years (Sections 3.2 and 6.4.1.1).
- The majority of the patients (~85%) are expected to be *TP53* wild type (WT); therefore, the overall results for this trial are expected to be driven by the outcome in the *TP53* WT population. To assess the efficacy of idasanutlin treatment, the assessment of secondary efficacy endpoints has been modified to limit testing within the *TP53* WT population only (Sections 2.2 and 3.3.2), with analysis of intent-to-treat population (all-patient population) as exploratory. In addition, the efficacy analysis section has been revised to reflect the updated study design (Section 6.4). The list of secondary and exploratory efficacy endpoints, as well as the list of outcome measures, have been modified (Sections 3.4, 6.4.2, and 6.4.3).
- To align with Section 4.4.2.2 of the protocol, a clarification has been added to the exclusion criterion that medications known to prolong the QT interval must be discontinued 7 days (or 5 half-lives, whichever is shorter) prior to initiating study medication until 5 days after the final administration of study medication (Section 4.1.2).
- A correction was made in the exclusion criteria from "irritable bowel disease" to "inflammatory bowel disease" (Section 4.1.2).
- Clarification has been made that written informed consent is necessary again for re-screening and must be obtained before any re-screening related tests and evaluations (Section 4.5.1 and Appendix 1).
- The hematologic malignancy response assessment criteria have been updated to align with 2017 European LeukemiaNet recommendations for diagnosis and management of AML in adults (Section 4.5.8).
- The pharmacodynamic and biomarker section has been updated to include *TP53* mutation status determination and to provide reference to the technical information of the assay used, [REDACTED] (Section 4.5.10.2).

- Clarification has been added that reporting of the adverse event of special interest thrombocytopenia (Grade $\geq$ 3 if associated with hemorrhage or bleeding) requires two separate adverse event of special interest forms to be completed (one for each of hemorrhage and thrombocytopenia) to facilitate complete safety analysis of patients experiencing thrombocytopenia Grade  $\geq$  3 concurrently with hemorrhage or bleeding (Section 5.2.3).
- Additional sensitivity analyses have been added in order to develop comprehensive interpretation of the data (Section 6.5).
- Language has been added for consistency with Roche's current data retention policy and to accommodate more stringent local requirements (if applicable) (Section 7.6).
- Language has been added to indicate that the study will comply with applicable local, regional, and national laws (Section 8.1).
- Clarification has been added that the adherence to protocol-mandated prophylaxis for diarrhea, emesis, and fungal and bacterial infections is applicable to all treatment cycles (Appendix 14).
- Emesis guidelines have been modified to clarify that 5-HT3-receptor antagonists with long half-life, such as palonosetron, may be taken on Day 1 only of the respective cycle (Appendix 14).
- The Medical Monitor names and associated contact information have been updated throughout the document.

Additional minor changes have been made to improve clarity and consistency.

Substantive new information appears in italics. This amendment represents cumulative changes to the original protocol.

## PROTOCOL SYNOPSIS

**TITLE:** A MULTICENTER, DOUBLE-BLIND, RANDOMIZED, PLACEBO-CONTROLLED, PHASE III STUDY OF IDASANUTLIN, AN MDM2 ANTAGONIST, WITH CYTARABINE VERSUS CYTARABINE PLUS PLACEBO IN PATIENTS WITH RELAPSED OR REFRACTORY ACUTE MYELOID LEUKEMIA (AML)

**PROTOCOL NUMBER:** WO29519

**VERSION NUMBER:** 6

**EUDRACT NUMBER:** 2014-003065-15

**TEST PRODUCT:** Idasanutlin (RO5503781)

**PHASE:** Phase III

**INDICATION:** Relapsed/Refractory Acute Myeloid Leukemia

**SPONSOR:** F. Hoffmann-La Roche Ltd

### **Objectives**

#### **Primary Objective**

The primary objective for this study is as follows:

##### **Within the TP53 wild type (WT) population**

- To compare overall survival (OS) in patients with relapsed or refractory acute myeloid leukemia (AML) who have been randomized to idasanutlin in combination with cytarabine versus those who have been randomized to cytarabine and placebo

#### **Secondary Objective**

The secondary objectives for this study are as follows:

##### **Within the TP53 WT population**

- To compare the proportions of complete remission (CR) between treatment arms
- To compare event-free survival (EFS) between treatment arms
- *To compare ORR (defined as CR), complete remission with incomplete platelet count recovery [CRp], and complete remission with incomplete blood count recovery [CRi] between treatment arms*
- *To compare duration of remission following CR (DOR) between treatment arms*
- To compare the proportions of allogeneic hematopoietic stem cell transplant (HSCT) following CR between treatment arms
- *To assess OS and CR in clinically actionable mutation-defined AML subpopulations, including FLT3, IDH1, and IDH2*
- *To assess the safety of idasanutlin plus cytarabine as compared with cytarabine and placebo*
- *To compare the differences in disease and treatment-related symptoms and health-related quality of life between treatment arms*

### Within the all-patient population

- To assess the safety of idasanutlin plus cytarabine as compared with cytarabine and placebo
- To characterize the pharmacokinetics of both idasanutlin and cytarabine
- To compare the differences in disease and treatment related symptoms and health-related quality of life between treatment arms

### **Exploratory Objective**

The exploratory objectives for this study are as follows:

### Within the all-patient population

- *To evaluate primary and secondary efficacy endpoints, including OS, CR, proportion of HSCT, EFS, and DOR in the all-patient population and OS and CR in the clinically actionable mutation-defined AML subpopulations (including FLT3, IDH1, and IDH2)*

### Within the all-patient and TP53 WT populations

- *To evaluate efficacy endpoints, including proportion of HSCT, CR, ORR, and DOR on the basis of response assessed over complete treatment period*
- *To evaluate LFS (leukemia-free survival, or duration of OR)*
- *To explore minimal/measurable residual disease (MRD) in the bone marrow after treatment with idasanutlin plus cytarabine compared with cytarabine and placebo*
- *To evaluate candidate response biomarkers (gene expression signatures) and murine double minute 2 (MDM2) protein expression in blast cells*
- *To assess prognostic and predictive effect of disease-associated mutations*

### **Study Design**

#### **Description of Study**

This is a Phase III multicenter, double-blind, randomized, placebo-controlled study of idasanutlin in combination with cytarabine compared with cytarabine and placebo.

A total of 440 patients with AML who have relapsed following, or are refractory to cytarabine-containing standard induction chemotherapy after at least one and no more than two prior cytarabine-containing induction chemotherapy regimen(s) are planned to be enrolled. Relapsed patients are defined as patients with first or second relapse; first relapsed patients who are young and had a good response to initial therapy (i.e. age <60 years with first CR achieved [CR1] duration > 1 year) are excluded. Refractory patients are defined as patients with persistent leukemia after one or two induction cycles, or patients with CR1 duration of < 90 days. Patients may have received prior HSCT in remission. Note that patients with prior allogeneic HSCT within 90 days prior to randomization will not be eligible for this study. The TP53 WT population will consist of patients with WT TP53, established centrally.

Re-screening is allowed under the conditions listed in the protocol.

Patients will be randomly assigned to each treatment arm. The arms will be stratified according to the following factors:

- Age (<60 years versus ≥60 years)
- Cytogenetic and molecular risk according to *the 2010 European LeukemiaNet (ELN)* standardized reporting system at initial diagnosis (favorable/intermediate versus adverse). Cytogenetic information allowing stratification in those two groups must be available.
- Response to initial anti-leukemic therapy (refractory versus CR ≥ 90 days but ≤ 1 year; versus CR > 1 year)
- Prior HSCT versus no prior HSCT

Patients will receive induction treatment with idasanutlin/placebo 300 mg twice daily (BID) and cytarabine 1 g/m^2 for 5 days followed by 23 days of rest (Cycle 1). For patients who achieve clinical response after induction and for whom HSCT for consolidation is not an option, it is

strongly recommended to continue study medication with a maximum of two additional cycles of consolidation (Cycles 2 and 3) unless clinically contraindicated

Responding patients, including those who proceed to HSCT, will be followed for EFS and *DOR*. All patients irrespective of response to treatment will be followed for OS until the end of the study.

An interim analysis for futility based on CR, EFS, and safety is planned after 120 *TP53 WT* patients are enrolled, have received at least one cycle, and confirmatory response assessment is available, to allow early stopping of the study in the event of inadequate CR, EFS, or safety concerns. The *futility* interim analysis will be performed by an independent Data Monitoring Committee (iDMC). Enrollment of patients will continue while *this* interim analysis takes place. If the Sponsor decides to stop the study based on iDMC recommendation following the *futility* interim analysis, enrollment will be discontinued.

*An efficacy interim analysis on OS is planned to be conducted by iDMC to allow early testing of OS in the event of relevant efficacy. The efficacy interim analysis will be conducted when 80% of the OS events have occurred (i.e., approximately 220 events). At this time, it is anticipated that all patients will have been enrolled.*

*Accompanying this interim efficacy analysis, a non-binding additional futility assessment will be performed based on a hazard ratio on overall survival  $\geq 1$ .*

*In the case of not reaching significance for OS at interim analysis, a primary analysis of OS will be performed (i.e., when 275 events have occurred).*

### **Number of Patients**

Overall, 440 patients with relapsed or refractory AML are expected to be enrolled in this study, over approximately 41 months.

### **Target Population**

#### Inclusion Criteria

Patients must meet the following criteria for study entry:

- Age  $\geq 18$  years
- Documented/confirmed first or second refractory or relapsed AML using World Health Organization classification, except acute promyelocytic leukemia. Please note that first relapsed AML patients with CR1 duration of  $> 1$  year AND age  $< 60$  years are excluded.
- No more than 2 prior induction regimens (excl. prior HSCT) in their first line treatment, and one must have included cytarabine with an anthracycline (or anthracenedione).
- Eastern Cooperative Oncology Group performance status of 0–2
- Adequate hepatic function assessed by the following:
  - Serum total bilirubin  $\leq 1.5 \times$  institutional upper limit of normal (ULN), unless resulting from hemolysis, Gilbert's syndrome, or liver infiltration with leukemia
  - AST/ALT  $\leq 3 \times$  institutional ULN (or  $\leq 5 \times$  upper limit of institutional laboratory reference range if liver infiltration with leukemia)
- Adequate renal function assessed by serum creatinine within reference laboratory ranges OR creatinine clearance (by Cockcroft Gault formula)  $\geq 50$  mL/min
- WBC count at randomization of  $\leq 50,000/\text{mm}^3$ 
  - Note: When treatment is not started immediately upon randomization, the WBC count at the start of induction therapy (Cycle 1) must remain at  $\leq 50,000/\text{mm}^3$ . The use of hydroxyurea (HU) or leukapheresis to meet eligibility is allowed. HU or leukapheresis must be discontinued at least 24 hours prior to the initiation of study medication.
- For women of childbearing potential: agreement to remain abstinent (refrain from heterosexual intercourse) or use two adequate methods of contraception, including at least one method with a failure rate of  $< 1\%$  per year, during the treatment period and for up to 6 months after the last dose of study drug

A woman is considered to be of childbearing potential if she has not reached a postmenopausal state ( $\geq 12$  months of amenorrhea with no identified cause other than

menopause), and has not undergone surgical sterilization (removal of ovaries and/or uterus).

Examples of contraceptive methods with a failure rate of < 1% per year include bilateral tubal ligation, male sterilization, and established, proper use of hormonal contraceptives that inhibit ovulation, hormone-releasing intrauterine devices, and copper intrauterine devices.

The reliability of sexual abstinence should be evaluated in relation to the duration of the clinical trial and the preferred and usual lifestyle of the patient. Periodic abstinence (e.g., calendar, ovulation, symptothermal, or postovulation methods) and withdrawal are not acceptable methods of contraception. Barrier methods must always be supplemented with the use of a spermicide.

- For men unless permanently sterile by bilateral orchidectomy: agreement to remain abstinent (refrain from heterosexual intercourse) or use contraceptive measures and agreement to refrain from donating sperm, as defined below:
  - With female partners of childbearing potential or pregnant female partners, men must remain abstinent or use a condom during the treatment period and for up to 6 months after the last dose of study drug. Men must refrain from donating sperm during this same period.
  - The reliability of sexual abstinence should be evaluated in relation to the duration of the clinical trial and the preferred and usual lifestyle of the patient.
- Ability to understand and willingness to sign a written informed consent form and comply with all study requirements including completion of patient-reported outcome measures.

#### Exclusion Criteria

Patients who meet any of the following criteria will be excluded from study entry:

- First relapsed patients aged <60 years with a CR1 duration of > 1 year
- Patients with prior documented antecedent hematological disorder including the following: myelodysplastic syndrome, myeloproliferative disease (i.e., chronic myelomonocytic leukemia, polycythemia vera, primary myelofibrosis, and essential thrombocythemia), and aplastic anemia
- AML secondary to any prior chemotherapy unrelated to leukemia
- Patients who are either refractory to or have relapsed within 90 days of receiving a regimen containing a cumulative dose of  $\geq 18$  g/m^2 cytarabine
- Patients who have received allogeneic HSCT within 90 days prior to randomization. HSCT should have been performed in remission and not used for salvage (patients who have received autologous HSCT as consolidation in CR1 are eligible).
- Patients who have received immunosuppressive therapy for graft-versus-host disease or for engraftment syndrome after autologous stem cell transplantation within 2 weeks prior to randomization
- Prior treatment with an MDM2 antagonist
- Patients with clinically relevant QTc prolongation (QT interval corrected using Fridericia's formula [QTcF] >480 ms), a family history of long QT syndrome, or who are currently receiving treatment with medications that are known to prolong the QT interval

*Medications that are known to prolong the QT interval must be discontinued 7 days (or 5 half-lives, whichever is shorter) prior to initiating study medication until 5 days after the final administration of study medication.*

- Patients receiving any other investigational or commercial agents or therapies administered with the intention to treat their malignancy within 30 days (or 5 half-lives) from first receipt of study drug
  - Note: The exception is HU or leukapheresis in patients who need to continue this therapy to maintain a WBC count  $\leq 50,000/\text{mm}^3$ . HU or leukapheresis must be discontinued at least 24 hours prior to the initiation of study medication.
- Patients with acute toxicities from any prior anti-leukemia therapy which have not resolved to Grade  $\leq 2$  per National Cancer Institute (NCI) Common Terminology Criteria for Adverse Events (CTCAE), Version 4.03
- Patients with a history of other malignancy within 5 years prior to screening, except for malignancy that has been in remission without treatment for at least 2 years prior to randomization
- Patients unable to temporarily interrupt treatment with moderate to strong CYP2C8 inducers and inhibitors (including gemfibrozil, which is also an inhibitor of UGT1A3), CYP2C8 or OATP1B1/3 substrates, or strong CYP3A4 inducers during the treatment phase. These agents must be discontinued 7–14 days prior to the start of study medication.
- Patients unable to temporarily interrupt treatment with oral or parenteral anticoagulants/anti-platelet agents (e.g., warfarin, chronic daily treatment with aspirin [ $> 325$  mg/day], clopidogrel, dabigatran, apixaban, rivaroxaban) during the treatment phase. These agents must be discontinued 7 days (or 5 half-lives) prior to the start of study medication.
  - Note: Treatment with or switch to low molecular weight heparin (LMWH) or unfractionated heparin (UFH) is allowed, according to local practice. However, platelet levels need to be closely monitored in these patients (see protocol).
- Patients with a history of systemic hypersensitivity reactions  $\geq$  Grade 2 attributed to cytarabine or components of the formulated product
- Patients who have any severe and/or uncontrolled medical conditions or other conditions that could affect their participation in the study, impair the ability of the investigator to evaluate the patient, or impair the patient's ability to complete the study such as the following:
  - Unstable angina, symptomatic or otherwise uncontrolled arrhythmia (does not include stable, lone atrial fibrillation), uncontrolled hypertension, symptomatic congestive heart failure (New York Heart Association III, IV), myocardial infarction  $\leq 6$  months prior to first study medication, and cerebrovascular accidents  $\leq 6$  months before study medication start
  - Unstable seizure disorders
  - Nonmalignant medical illnesses that are uncontrolled or whose control may be jeopardized by this study medication, such as hereditary coagulation disorders or insulin-dependent diabetes mellitus not optimally controlled with medical management (e.g., presence of ketoacidosis) or active gastrointestinal (GI) conditions (e.g., Grade  $\geq 2$  graft-versus-host disease) and uncontrolled *inflammatory* bowel disease (i.e., Crohn's disease, ulcerative colitis, diverticulosis-associated colitis, and Behçet's disease).
- Infection considered by the investigator to be clinically uncontrolled or of unacceptable risk to the patient upon the induction of neutropenia, that is, patients who are or should be on antimicrobial agents for the treatment of active infection such as the following:
  - Fungal infection with visceral involvement, other than mucosal candidiasis, with  $< 2$  weeks of appropriate systemic antifungal therapy
  - Active bacterial infection and/or bacterial infection with positive cultures in the 7 days prior to dosing
  - Patients who have received  $< 5$  days of appropriate therapeutic antibiotic therapy for an identified infection

History of symptomatic *Clostridium difficile* infection that required treatment within 1 month prior to dosing. Upon clinical response to *C. difficile* treatment, the stool consistency and frequency must have returned to normal.

In all cases, the patient should be afebrile (exception of AML-related fever) and hemodynamically stable for at least 72 hours at the time of study medication initiation.

- Patients with a history of active or chronic infectious hepatitis unless serology demonstrates clearance of infection

Patients with occult or prior hepatitis B virus (HBV) infection (defined as negative hepatitis B surface antigen and positive total hepatitis B core antibody) may be included if HBV DNA is undetectable, provided that they are willing to undergo monthly DNA testing. Patients who have protective titers of hepatitis B surface antibody after vaccination or prior but cured hepatitis B are eligible. Patients positive for hepatitis C virus antibody are eligible provided polymerase chain reaction (PCR) is negative for HCV RNA.

- Patients who have a history of clinically significant liver cirrhosis (e.g. Child-Pugh class B and C).
- Patients with electrolyte abnormalities such as hypokalemia, hyperkalemia, hypocalcemia, hypercalcemia, hypomagnesemia, and hypermagnesemia of Grade > 1 per NCI CTCAE v4.03. Treatment for correction of above electrolyte imbalances is permitted during screening to meet eligibility.
- Patients with extramedullary AML with no evidence of systemic involvement
- Patients with active CNS leukemia
- Pregnant or breastfeeding patients
- HIV-positive patients
- Patients who might refuse to receive blood products and/or have a hypersensitivity to blood products

### **End of Study**

The end of this study is defined as the date when the last patient, last visit (LPLV) occurs. LPLV is expected to occur 2 years after the last patient is enrolled or after all patients have died, whichever occurs first.

### **Length of Study**

The total length of the study, from screening of the first patient to the end of the study, is expected to be approximately 5.5 years.

### **Investigational Medicinal Products**

#### **Test Product (Investigational Drug)**

Idasanutlin/placebo will be administered at 300 mg BID orally, without regard to meals. Water can be given ad libitum.

In case the patient proceeds to consolidation therapy, only 50% of idasanutlin should be given (300 mg once daily [QD] in the morning).

Cytarabine will be administered at a dose of 1 g/m^2 QD as a 1–3 hour intravenous infusion. In case the patient proceeds to consolidation therapy the dose may need to be reduced to 50% (0.5 g/m^2 QD).

### **Statistical Methods**

#### **Efficacy Analysis**

Patients will be analyzed according to the treatment arm to which they were randomized. *The TP53 WT population is the efficacy population and refers to all randomized TP53 WT patients as identified by a central laboratory test.*

*Description of efficacy analysis in this section is valid for both interim and primary analysis.*

### Primary Efficacy Endpoint

The primary efficacy endpoint, OS, is defined as the time from randomization to death due to any cause. OS for patients who have not died at the time of the analysis will be censored at the date last known alive.

*The primary OS analysis of the study will assess the null hypothesis of equality of OS functions in the idasanutlin in combination with cytarabine (MDM2-chemo) arm versus the cytarabine given with a placebo (chemo) arm in the TP53 WT population as follows:*

H0:  $OS_{MDM2-chemo} = OS_{chemo}$  versus H1:  $OS_{MDM2-chemo} \neq OS_{chemo}$

A formal treatment comparison will be made using a two-sided stratified log-rank test at a significance level defined using the O'Brien-Fleming alpha-spending function with overall Type I error rate at 0.05 corresponding to available information. Stratification factors that will be used are the same as for randomization, i.e. age (<60 versus  $\geq 60$  years), cytogenetic and molecular risk (favorable/intermediate versus adverse), prior response to initial anti-leukemic therapy (refractory versus CR  $\geq 3$  months but  $\leq 1$  year versus CR > 1 year) and prior HSCT versus no prior HSCT.

Survival curves in each treatment arm will be estimated using Kaplan–Meier estimates. The Kaplan–Meier estimates will provide a visual description of the survival curves and the difference across treatment arms. The treatment effect will be quantified via a hazard ratio, computed from a stratified Cox proportional-hazards regression, including a 95% CI. To further describe and quantify OS, estimated median OS per arm and 1-year and 2-year survival probabilities, all including 95% CI, will be given. The effect of prognostic factors on OS will be assessed in an exploratory analysis using Cox multivariate regression.

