### Efficacy

*An interim analysis for efficacy on OS is planned to be conducted by iDMC. The efficacy interim analysis will be conducted when 80% of the OS events have occurred (i.e., approximately 220 events). At this time, it is anticipated that all patients will have been enrolled.*

*For the interim efficacy analysis of OS, the significance level will be determined using the O'Brien-Fleming alpha-spending function with overall type I error rate at 0.05 level. At the time of the interim efficacy analysis, it is expected that 80% of the OS events will have occurred, corresponding to an alpha spending of 0.025 for the interim and 0.043 for the final OS analysis leading to a power of 83% for the final analysis.*

*The iDMC will test OS for efficacy and check if there is a significant difference (alpha level 0.025 or as assessed based on actual number of OS events) in OS in favor of the experimental arm.*

*Accompanying this interim efficacy analysis, a non-binding additional futility assessment will be performed and the iDMC may recommend stopping the study for futility if the hazard ratio on overall survival is greater than or equal to one.*

*Further details of the interim analyses will be described in the iDMC Charter and Statistical Analysis Plan.*

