##### **4.4.1 Primary Efficacy Endpoint**

The OS analysis will assess the null hypothesis of equality of OS distributions in the idasanutlin+cytarabine and placebo+cytarabine treatment arms in *TP53* WT patients:

$H_0: OS_{\text{idasanutlin+cytarabine}} = OS_{\text{placebo+cytarabine}}$  versus  $H_1: OS_{\text{idasanutlin+cytarabine}} \neq OS_{\text{placebo+cytarabine}}$

OS distributions will be compared between the treatment groups using a 2-sided stratified log-rank test at an overall significance  $\alpha$  level of maximum 4%. The stratification factors will be the randomization stratification factors: age (<60 years vs.  $\geq 60$  years), cytogenetic and molecular risk (favorable/intermediate vs. adverse), prior response to initial anti-leukemic therapy (refractory vs. CR  $\geq 3$  months but  $\leq 1$  year vs. CR > 1 year) and prior HSCT versus no prior HSCT. The IWRS data will be compared with the eCRF data for each patient. For cases where there is a difference between the IWRS and eCRF data, the stratification factors as entered in the eCRF will be used in the primary endpoint analysis.

The OS survival curves in each treatment arm will be estimated using Kaplan-Meier methodology and summarized using Kaplan-Meier plots. The treatment effect of idasanutlin+cytarabine versus placebo+cytarabine will be expressed as an HR using a stratified Cox proportional-hazard regression, including a 95% CI. In addition to the OS HR, 6-monthly OS probabilities and the estimated median OS in each arm (if reached) will be presented, including 95% CI.

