#### **4.11.3 Efficacy Interim Analysis**

At the time of the efficacy interim analysis (on OS) that will be conducted when 80% of the events have occurred (i.e., approximately 220 events), it is

anticipated that all patients have been enrolled. OS will be tested at the significance level determined using the O'Brien-Fleming alpha-spending function so the overall Type I error rate will be maintained at the 0.05 level. With 80% information, the alpha spending is 0.024.

The iDMC may recommend unblinding the study for efficacy if there is a significant difference in OS in favor of the experimental arm (alpha level 0.024 or as assessed based on actual number of OS events).

Accompanying this interim efficacy analysis, a non-binding additional futility assessment will be performed and the iDMC may recommend stopping the study for futility if the hazard ratio on overall survival is greater than or equal to one.

Further details about the interim analyses will be described in the iDMC Charter.

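### OS is tested at about 0.024 and 0.043 but its hazard ratio is reported only with a plain 95% CI; an interval at each look's own level would be a cheap improvement

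*Protocol*

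**What the plan says.** The protocol (synopsis and 6.4.1) ties the OS test to the sequential design: "A formal treatment comparison will be made using a two-sided stratified log-rank test at a significance level defined using the O'Brien-Fleming alpha-spending function". The same section gives the estimate: "The treatment effect will be quantified via a hazard ratio, computed from a stratified Cox proportional-hazards regression, including a 95% CI". SAP 4.4.1 agrees: the effect "will be expressed as an HR using a stratified Cox proportional-hazard regression, including a 95% CI". The protocol's efficacy section adds: "Description of efficacy analysis in this section is valid for both interim and primary analysis". The 95% CI is therefore the planned interval at both looks.

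The stated test levels are not uniform:

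- Protocol 6.11.2: "corresponding to an alpha spending of 0.025 for the interim and 0.043 for the final OS analysis".
- SAP 4.11.3: "With 80% information, the alpha spending is 0.024".
- SAP 4.4.1 sets the OS test at a "level of maximum 4" percent.

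Neither document plans an interval at the level of the look, or any adjustment or caveat for an HR reported after an early stop. SAP Section 2 and 2.4 do plan an updated OS analysis at the end of the study.

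**The concern.** A 95% CI excludes 1 exactly when the corresponding two-sided test gives p < 0.05. OS succeeds only at a stricter level, so an HR can have a 95% CI below 1 while OS has not met its boundary. Under SAP 4.4.2 all 11 secondary hypotheses then stay untested, and a reader sees an apparently positive interval on a failed primary endpoint.

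An HR reported because it crossed an early boundary has also been selected for being extreme, so on average it overstates the benefit. Under the planned effect, crossing at the interim is the likelier outcome.

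**Working it through.** **Inputs.** 220 and 275 deaths, 80% information, 2:1 allocation, overall two-sided 0.05, O'Brien-Fleming spending, planned HR 0.67 with 85% power, and 83% after the interim was added (Protocol 4.2, 6.1, 6.11.2; SAP 2.3, 4.11.3).

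**1. The plan's own figures.**

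- Interim level, with 0.025 spent per side: 2[1 − Φ(2.2414/√0.8)] = 0.0122 per side, or 0.0244 two-sided (z = 2.250).
- Final level: solve P(Z1 < 2.250, Z2 < c) = 0.975 with correlation √0.8. This gives c = 2.025, or 0.0429 two-sided. The results match the SAP's 0.024 and the protocol's 0.043; the protocol's 0.025 is slightly high.
- Minimum detectable HR: exp(−1.96/√(275 × 2/9)) = exp(−1.96/7.817) = 0.778, and 6/0.778 = 7.7 months. The plan states 0.78 and 7.7.
- Power: simulating the plan's responder and long-term-survivor model gives 85.3% at 0.05 and 83.1% at 0.043. The plan states 85% and 83%.
- The single HR with 85% power at 275 deaths is exp(−(1.960 + 1.036)/7.817) = 0.68. I use it as the effective planned effect.

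**2. Where test and interval part.** Take information = deaths × 2/9, so √information is 6.992 at 220 deaths and 7.817 at 275.

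| Look | OS test met at HR ≤ | 95% CI excludes 1 at HR ≤ |
|---|---|---|
| 220 deaths | exp(−2.250/6.992) = 0.725 | exp(−1.96/6.992) = 0.756 |
| 275 deaths | exp(−2.025/7.817) = 0.772 | exp(−1.96/7.817) = 0.778 |

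At the SAP's 4% the final test threshold is 0.769.

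Example at 275 deaths: an observed HR of 0.775 has p = 0.046, which fails at 0.043. Its 95% CI is 0.603 to 0.996; the matched 95.7% CI is 0.598 to 1.004.

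**3. Frequencies.** Normal approximation to the log HR, 4 million two-look trials per row, non-binding futility ignored. The gap is the chance that the 95% CI excludes 1, in either direction, without the boundary being met. Early stops are those in favor of idasanutlin; their mean HR is geometric.

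| True HR | Gap, interim | Gap, final | Stop early | Mean HR if stopped | 95% CI coverage, all trials | 95% CI coverage, early stops |
|---|---|---|---|---|---|---|
| 0.67 | 9.1% | 1.2% | 71% | 0.625 | 95.0% | 96% |
| 0.68 | 9.7% | 1.3% | 67% | 0.63 | 95.0% | 96% |
| 0.80 | 10.0% | 2.2% | 25% | 0.67 | 95.0% | 90% |
| 0.90 | 4.8% | 1.2% | 6.5% | 0.68 | 94.7% | 62% |
| 1.00 | 2.6% | 0.6% | 1.2% | 0.69 | 94.4% | 0% by construction |

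Under no effect, only 0.3% of trials fall in the final gap in the favorable direction.

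**4. After the change.** With each look's own level, overall coverage is 95.0% under no effect and 96.4% to 96.6% at the other HRs shown. Relative widths on the log scale are 2.250/1.96 = 1.15 and 2.025/1.96 = 1.03.

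**The case against.** The strongest reply is that nothing is decided by the interval. OS success rests on the log-rank test at the spending-function level, and the secondary hierarchy opens only on that rejection. Type I error is untouched. This stands.

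A reader might infer from the two interim rows of the comparison that roughly one trial in ten would publish an interval contradicting its test. The documents do not support that. A trial that crosses at the interim has p below 0.0244, so its 95% CI must exclude 1. An interim that does not cross is seen by arm only by the iDMC and its independent coordinating center (Protocol 4.2, SAP 4.11). The reportable conflict is confined to the final look.

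A reader might also infer that the 95% CI covers badly. Overall it does not, and among early stops at the planned effect it covers about 96%. Conditional coverage is poor only when the true effect is much weaker, where early stops are uncommon.

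Part of the exaggeration would exist without an interim look. A single analysis at 275 deaths, selected for p < 0.05, has a mean HR of 0.657 when the truth is 0.68. On the log scale that is (0.420 − 0.386)/(0.462 − 0.386) = 45% of the early-stop inflation. Averaged over all outcomes, the reported HR is 0.673 against 0.68. The planned end-of-study update also means that the interim HR need not be the only OS estimate, although it does not remove the selection.

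**Conclusion.** The gap in the specification is real and its practical size is modest, so this is a cheap improvement and not a flaw in the design. At neither look does the planned interval match the test. In reported results this matters in a narrow final-look band, HR about 0.772 to 0.778: about 1% of trials at the planned effect and about 2% at most. If the SAP's 4% governs, the band widens to 0.769 to 0.778.

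The early-stop exaggeration is an average over stopped trials, not a certainty in any one: about 0.63 for a true 0.68, or 0.462/0.386 = 1.20 times the log effect.

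These figures assume exactly 220 and 275 deaths, information of deaths × 2/9, approximate normality of the log HR, and a constant HR. The plan's long-term-survivor model departs from a constant HR. Simulated directly, with a one-step log-rank estimate of the HR, it crosses at the interim in 65% of trials with a mean HR of 0.61, which is the same picture.

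**What to change.** 1. Reconcile the levels first: 0.025 and 0.043 in Protocol 6.11.2, 0.024 in SAP 4.11.3, and the 4% maximum in SAP 4.4.1. A matching interval cannot be written until one set governs.
2. In Protocol 6.4.1 and SAP 4.4.1, report the OS HR with the CI at that look's own spending-function level: about 97.6% at 220 deaths and 95.7% at 275, recomputed from the actual event counts. Keep the plain 95% CI, labeled descriptive.
3. If OS crosses at the interim, state beside the HR that it tends to overstate the effect, and report the planned end-of-study OS update with it.

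A median-unbiased HR from stage-wise ordering is not worth specifying for an interim stop. This is the first efficacy look, so that estimate equals the ordinary HR and corrects nothing. The wider interval does not remove the exaggeration either, which is why the caveat is needed.

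The cost is a few lines of text and intervals about 15% wider at the interim and 3% wider at the final look on the log scale. Sample size, boundaries and trial conduct do not change.
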